8.2.5 Sponsor Responsibility for Reporting Adverse Events

All Adverse Events will be reported to regulatory authorities, IRB/IECs and investigators in accordance with all applicable global laws and regulations.

8.2.6 Tumor Biopsies/Archival Tissue Collection

Provision of tissue from an archival tissue sample or newly obtained core or excisional biopsy of a tumor lesion will be encouraged.

- a. For archival tissue, 10 unstained slides of 4-5 micron thickness on positively charged slides are required.
- b. Tumor tissue may be from a diagnostic biopsy or a portion of a surgical specimen, if surgery is a component of definitive intent therapy.
- c. Formalin fixed paraffin embedded (FFPE) tissue samples are acceptable; a fine needle aspirate, frozen sample, plastic embedded sample, cell block, clot, bone, bone marrow or cytologic specimen will not be acceptable for IHC analysis.
- d. It is recommended that FFPE blocks be sectioned fresh (within 7 days of sectioning and sending for PD-L1 analysis) onto positively charged slides; slides should be stored and shipped (and stored upon receipt at Qualtek) at 2-8C in the dark.
- e. Recommended fixation time for samples is 24 hours to 48 hours in 10% neutral buffered formalin.

9 Statistical Plan

9.1 Statistical Analysis Plan Summary

The statistical analysis of the data obtained from this study will be the responsibility of the Biostatistics Core Facility of the Abramson Cancer Center.

Objectives of the study are stated in Section 3.

9.2 Sample Size Determination

The sample size will be 41 evaluable patients; i.e.: subjects who receive at least 1 dose of proton reirradiation.

9.3 Hypothesis/Evaluation

This phase II study evaluates a multi-stage treatment plan for recurrent disease that is comprised of definitive therapy consisting of proton reirradiation with or without chemotherapy, followed by consolidation Pembrolizumab, for recurrent NSCLC. A total of 41 patients will be enrolled on the study. Between the end of definitive therapy and the start of Pembrolizumab, there is a 4-12 week rest period. The primary intent-to-treat analysis will estimate PFS from start of definitive therapy, regardless of whether consolidation Pembrolizumab was administered. A secondary proof of principle analysis will estimate PFS in the subgroup of patients who receive definitive therapy followed by consolidation Pembrolizumab. The benefit of adding Pembrolizumab after definitive therapy will be determined in this analysis, by testing whether PFS is improved as compared to a historical control population who received standard therapy only. For this proof of principle analysis, the null hypothesis is that the median PFS from start of therapy for a recurrence of NSCLC is 6 months as compared to the alternative hypothesis that the median PFS is increased to 10 months.

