5.2 Treatment Regimen

Patients will be treated with reirradiation with or without standard concurrent chemotherapy to all gross disease with proton beam therapy. The intended radiation dose should be at least 60 Gy of reirradiation in 1.8-2.0 Gy fractions with or without concurrent chemotherapy or in 4.0 Gy fractions without chemotherapy, at the provider's discretion. This corresponds to daily fractionated radiation over a period of approximately 3-8 weeks. The decision to use concurrent chemotherapy, and which regimen to utilize, are left to the discretion of the treating oncologist. The chemotherapy regimen and doses will be recorded in the patient record.

Pembrolizumab will be started 4 to 12 weeks after completion of reirradiation. Pembrolizumab will be given at a dose of 200 mg intravenously approximately every 21 days for 17 cycles (about 12 months) if there is no evidence of progressive disease or intolerable side effects.

Dose Modifications (Escalation/Titration/Other)

Adverse events (both non-serious and serious) associated with pembrolizumab exposure may represent an immunologic etiology. These adverse events may occur shortly after the first dose or several months after the last dose of treatment. Pembrolizumab must be withheld for drug-related toxicities and severe or life-threatening AEs as per 3 below. See Section 5.6 for supportive care guidelines, including use of corticosteroids.

Table 1: Dose Modification Guidelines for Drug-Related Adverse Events

Toxicity	Hold Treatment For Grade	Timing for Restarting Treatment	Treatment Discontinuation
Diarrhea/Colitis	2-3	Toxicity resolves to Grade 0-1	Toxicity does not resolve within 12 weeks of last dose or inability to reduce corticosteroid to 10 mg or less of prednisone or equivalent per day within 12 weeks
	4	Permanently discontinue	Permanently discontinue
AST, ALT, or Increased Bilirubin	2	Toxicity resolves to Grade 0-1	Toxicity does not resolve within 12 weeks of last dose
	3-4	Permanently discontinue (see exception below) ^a	Permanently discontinue
Type 1 diabetes mellitus (if new onset) or Hyperglycemia	T1DM or 3-4	Hold pembrolizumab for new onset Type 1 diabetes mellitus or Grade 3-4 hyperglycemia associated with evidence of beta cell failure	Resume pembrolizumab when patients are clinically and metabolically stable

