8.1.5.3 Pre-Pembrolizumab Screening

Visit requirements are outlined in Section 7.0 - Trial Flow Chart.

Subjects will be eligible to move on to pembrolizumab treatment cycles if they received at least 50 Gy of reirradiation, if they have no progressive disease on tumor imaging, and if they do not have symptomatic CTCAEv5 grade ≥ 3 pneumonitis.

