9.4 Statistical Methods

Primary Objective

1. The primary intent-to-treat analysis will estimate progression free survival from initiation of definitive therapy by the Kaplan-Meier method. Median PFS and 95% CI will be determined. A total of 41 patients will be enrolled on the study.
2. A secondary proof of principle analysis will determine the clinical benefit of adding consolidation Pembrolizumab after definitive therapy. Only patients who receive consolidation Pembrolizumab are included in this analysis. It is expected that up to 15% of enrolled patients will have progressive disease or lingering toxicity and will not start Pembrolizumab after definitive therapy. Thus we anticipate that at least 35 patients will be included.

In this proof of principle analysis, we will compare progression free survival from initiation of definitive therapy to a historical control value. We assume the median PFS for the historical control population treated with standard therapy only is 6 months and the median PFS for the patients treated with definitive therapy and consolidation Pembrolizumab is 10 months. Assuming 35 patients are enrolled over 2 years and followed for an additional 3 months, the final analysis will have 80% power to detect an improvement in median PFS assuming exponential survival and 1-sided 5% significance level.

Secondary Objectives

1. Overall survival will be estimated by the Kaplan-Meier method. Median OS and 95% CI will be determined.
2. Toxicities will be graded, categorized and tabled. For the definitive therapy phase, we will report on adverse events which are grade 3 or higher treatment-related toxicities or any grade of pneumonitis or esophagitis. For the Pembrolizumab phase, we will report all treatment-related toxicities.

Exploratory Objective

1. Biomarkers will be tested for association with PFS using log rank test for categorical biomarkers and Cox proportional hazards regression for continuous biomarkers. Biomarkers will be tested for association with graded toxicity (i.e., worse toxicity grade) for specific categories of toxicity using chi square test for categorical biomarkers and Spearman's correlation for continuous biomarkers.

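### The secondary test in pembrolizumab starters cannot show the benefit of adding pembrolizumab: starters carry guaranteed progression-free time, and the 6-month benchmark has no source

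*Combined protocol and SAP*

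**What the plan says.** Section 9.3 states that "The benefit of adding Pembrolizumab after definitive therapy will be determined in this analysis". Section 9.4 repeats the claim: "A secondary proof of principle analysis will determine the clinical benefit of adding consolidation Pembrolizumab after definitive therapy". The method that Section 9.3 gives for reaching this conclusion is a historical comparison, "by testing whether PFS is improved as compared to a historical control population who received standard therapy only".

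The benchmark in Section 9.3 is that "the null hypothesis is that the median PFS from start of therapy for a recurrence of NSCLC is 6 months". Section 9.4 introduces the same value as an assumption: "We assume the median PFS for the historical control population treated with standard therapy only is 6 months". No reference is attached to it in either section, or in the Study Summary, which calls it a historical rate.

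The analysis set is limited to patients who receive pembrolizumab, at least 35 of 41 expected, while PFS runs from the start of definitive therapy (Sections 9.3.1 and 9.4). Section 8.1.5.3 lets patients go on to pembrolizumab only "if they have no progressive disease on tumor imaging", with at least 50 Gy delivered and without symptomatic grade 3 or higher pneumonitis. On timing, Section 5.2 says of the radiation: "This corresponds to daily fractionated radiation over a period of approximately 3-8 weeks". It then says: "Pembrolizumab will be started 4 to 12 weeks after completion of reirradiation".

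The primary analysis takes all enrolled patients and only estimates the median with a 95% CI. The Study Summary attaches the same 6-versus-10-month power statement to 41 patients. This point concerns the test as Sections 9.3 and 9.4 define it.

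**The concern.** The clock starts at reirradiation, but a patient enters the analysis only by reaching the first pembrolizumab dose without progression. The interval before that dose is therefore progression-free by construction, up to the timing of the qualifying scan. The 6-month benchmark is also counted from the start of therapy, and the documents do not say that it was derived from patients who passed a similar landmark. If it was not, the two sides of the comparison differ even when the drug does nothing.

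As Sections 9.3 and 9.4 are worded, a rejection would be reported as benefit from adding pembrolizumab. It could come from leaving out early progressors, or from a 6-month value that does not describe definitive therapy alone. No other analysis in Section 9 has an efficacy null and a power statement, so its stated conclusion will carry weight.

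**Working it through.** **Inputs.** From Section 9.4: 35 patients, 24 months of accrual plus 3 months of follow-up, medians of 6 and 10 months, exponential PFS, one-sided 5%, up to 15% non-starters. From Section 5.2: radiation over 3-8 weeks, then a gap of 4-12 weeks.

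**1. The plan's power figure.** With hazard λ = ln 2 / median, the chance of an observed event is 1 − [exp(−3λ) − exp(−27λ)] / (24λ). This is 0.761 at a median of 6 months and 0.604 at 10 months. Expected events are 35 × 0.761 = 26.6 and 35 × 0.604 = 21.1. Power on the log-hazard scale is Φ[(ln(10/6) − 1.645/√26.6) × √21.1] = Φ(0.88) = 0.81. The stated 80% is reproduced, so the power arithmetic is not the fault.

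**2. Where the start of pembrolizumab falls.** Earliest 3 + 4 = 7 weeks (1.61 months), latest 8 + 12 = 20 weeks (4.60 months) after time zero.

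**3. What the plan's own null implies by then.** Progressed or dead by week 7: 1 − exp(−ln 2 × 1.61/6) = 17%. By week 20: 1 − exp(−ln 2 × 4.60/6) = 41%. Under the exponential model, patients known to be event-free at 1.61 months have a median from time zero of 6 + 1.61 = 7.6 months with no drug effect.

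**4. False-positive risk with no drug effect and a true median of exactly 6 months.** Simulation with 40,000 trials per row and a one-sample log-rank test of observed events O against the number E expected under the 6-month exponential, rejecting if z < −1.645. Section 9.4 names no test statistic, so each range covers z = (O − E)/√E and z = (O − E)/√((O + E)/2). The 15% non-starters correspond to 6 of 41 (0.85 × 41 = 34.9).

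| Who is left out | Rejection |
|---|---|
| Six of 41, unrelated to outcome | 4-5% |
| Three earliest progressors and three unrelated | 10-13% |
| Six earliest progressors | 23-27% |
| Everyone with an event before week 7 (35 starters) | 27-32% |
| As the row above, counting events and time only from week 7 | 4-5% |

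The last row shows that the excess comes from the guaranteed time.

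**5. Dependence on the model.** With the median kept at 6 months, an assumed Weibull shape of 1.5 and E taken from that curve, the 7-week row falls to about 11-14%. Early events are then rarer: 1 − exp(−ln 2 × (1.61/6)^1.5) = 9% by week 7.

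**6. The benchmark.** The documents give no treatment details, population or source for the 6 months. The one median PFS given for proton reirradiation is 14 months, in Section 1.1, from an initial cohort with low-volume targets.

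**The case against.** The analysis is labelled secondary and proof of principle, single-arm phase II trials commonly use historical controls, and the unselected intention-to-treat median will be reported beside it. All of that stands and limits the harm. It does not change the two sentences, which say that this analysis determines the drug's benefit.

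Four stronger readings are tempting, and the documents do not support them.

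- *The historical patients had some other treatment, so proton reirradiation is itself a confounder.* The more natural reading of the comparator label is definitive therapy without the drug. A footnote in Section 7.1 sets the 42-day baseline imaging window before standard-of-care treatment, and Section 8.1.2.6 sets the same window before the first day of proton reirradiation. What remains is that nothing supports 6 months for that treatment.
- *The true no-drug median is 14 months, so 6 is wrong.* That figure comes from a low-volume cohort. It shows that the value is uncertain and is not a replacement null.
- *The historical group is known to be unselected.* The documents do not describe how it was selected. If it met the same landmark, the guaranteed-time bias would not arise.
- *The false-positive risk is at least 27%.* That row needs a constant hazard from day 0. It removes 17% as early events, against a planning figure of up to 15% for progression and toxicity together. The qualifying scan may also precede the first dose by up to about 30 days (Section 8.1.2.6).

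In the other direction, the 15% is an expectation and does not cap the selection: the plan's own exponential null implies 17% with events by the earliest start. If the 25-treatment minimum in Section 9.3.2 applies to this set, the earliest start would also be later than week 7. That minimum was not modelled.

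**Conclusion.** The concern holds in limited form. The test in starters cannot determine the benefit of adding pembrolizumab, because membership of the analysis set depends on remaining progression-free after time zero and the benchmark is not stated to share that condition. With no drug effect and a true median of exactly 6 months, the nominal 5% test rejects in 4-5% of trials when non-starting is unrelated to outcome and in up to 23-27% within the protocol's own 15% non-starters. The 7-week condition gives 27-32% with exponential PFS and about 11-14% with the assumed Weibull curve. The direction of the bias is clear if the historical group did not pass a similar landmark. Its size depends on the hazard shape and on how many non-starters are early progressors.

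The missing source for the 6 months is a separate gap and cannot be sized from the documents. A reader might infer that the trial's main result is compromised. It is not, because the primary intention-to-treat analysis includes all enrolled patients and only estimates the median.

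**What to change.** Replace the two statements in Sections 9.3 and 9.4 with wording such as:

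> This secondary analysis compares PFS of the full regimen (proton reirradiation with or without chemotherapy, then pembrolizumab), in patients who remain progression-free and start pembrolizumab, with an external 6-month benchmark. It does not isolate the contribution of pembrolizumab, and rejection will not be reported as evidence of benefit from adding it.

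Also state the treatment, population and source behind the 6 months, including whether those patients had to be progression-free at a landmark.

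If a test in starters is kept, leave time zero where it is but count observed and expected events only from each patient's pembrolizumab start (delayed entry). Each patient's expected count is then the null cumulative hazard at exit minus that at entry. This removes the guaranteed-time bias if the null curve is right. It does not remove selection on toxicity or delivered dose, and it does not correct a wrong benchmark. With a 7-week start, power at a 10-month median is about 75-79% instead of 78-81%.

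The cost is two reworded sentences, one added definition with its source, and a narrower, less favourable claim. Sample size and trial conduct do not change.

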Isolated local or regional recurrences of non-small cell lung cancer (NSCLC) in or near previously irradiated thoracic fields present a therapeutic challenge. Rather than using systemic therapy alone, instituting localized therapy is appealing given our generally poor response rates to salvage chemotherapy, particularly in tumors that arise in previously irradiated fields. However, surgery and radiation therapy are both technically difficult and pose high toxicity risks in this setting. Conventionally fractionated thoracic reirradiation for recurrent lung cancer has yielded 1-year local progression-free survival (PFS) rates as high as 51% [1-6], but its widespread use has been limited by toxicities. Given these positive results, proton reirradiation has been utilized as a potential strategy to minimize harm to surrounding tissues while treating a local recurrence aggressively. A multicenter study presented at the 2013 ASCO Annual Meeting reported encouraging early outcomes, with a median PFS of 14 months, and acceptable toxicity for proton reirradiation in an initial cohort of patients treated with low-volume clinical target volumes [7]. Since proton reirradiation is a promising new tactic to treat thoracic recurrences of NSCLC that can potentially minimize toxicities compared with photon reirradiation, additional strategies to improve outcomes with this modality are warranted.

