4.1 Inclusion Criteria

1. Histologic or cytologic diagnosis of NSCLC who have received previous intrathoracic radiation therapy with definitive intent and have a tumor recurrence in or near the prior irradiation fields.

Phase II Pembrolizumab Reirradiation

Re-biopsy of the recurrence is not required and is left to the discretion of the treating physician, although every effort should be made to confirm recurrence pathologically.

2. Eastern Cooperative Oncology Group (ECOG) performance status of 0-1
3. Age 18 or greater
4. Patients with prior invasive malignancies are allowed, provided they have been treated with definitive intent and have no evidence of active disease requiring treatment in the past 2 years.
5. Patients must be capable of giving informed consent and be willing and able to comply with schedule.
6. Serum total bilirubin \leq 1.5 X upper limit of normal (ULN) OR Direct bilirubin \leq ULN for subjects with total bilirubin levels $>$ 1.5 ULN prior to Pembrolizumab treatment.
7. Platelets $>100,000$ cells/mm³ and ANC $\geq 1,250$ cells/mm³ prior to Pembrolizumab treatment.
8. Creatinine \leq 1.5 X ULN OR measured or calculated creatinine clearance ≥ 50 mL/min for subject with creatinine levels $>$ 1.5 X institutional ULN. (GFR can also be used in place of creatinine or CrCl) prior to Pembrolizumab treatment
9. Clinical target volume (CTV) size must be <250 cc, no more than 74 Gy of prior radiation in 2 Gy fractions previously administered.

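### Rejecting the 6-month null cannot show a benefit of adding pembrolizumab: the control is unsourced and is not reconciled with the 14-month median PFS the protocol cites for proton reirradiation

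*Combined protocol and SAP*

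**What the plan says.** Section 9.3 describes a primary intention-to-treat analysis that estimates PFS, and a secondary proof-of-principle analysis limited to patients who start pembrolizumab. Of the secondary analysis it says: "The benefit of adding Pembrolizumab after definitive therapy will be determined in this analysis". The hypotheses follow: "the null hypothesis is that the median PFS from start of therapy for a recurrence of NSCLC is 6 months"; under the alternative the median is 10 months. Section 9.4 describes the control: "We assume the median PFS for the historical control population treated with standard therapy only is 6 months". It gives 80% power for 35 patients, with 2 years of accrual, 3 further months of follow-up, exponential survival and a one-sided 5% level. Neither section cites a source for 6 months or names the test statistic. The Study Summary presents the 6-versus-10 comparison for 41 patients without the secondary label.

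Section 1.1 (Background) reports a multicenter proton reirradiation study "with a median PFS of 14 months, and acceptable toxicity for proton reirradiation in an initial cohort of patients treated with low-volume clinical target volumes". It also says that conventionally fractionated thoracic reirradiation "has yielded 1-year local progression-free survival (PFS) rates as high as 51" per cent. Section 4.1, item 9, requires: "Clinical target volume (CTV) size must be <250 cc". Under Sections 3.1 and 5.2 every patient receives proton reirradiation, with or without chemotherapy, before pembrolizumab.

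**The concern.** A single-arm test can attribute a gain to an added drug only if the null describes the same backbone without that drug. The backbone here is proton reirradiation in targets under 250 cc. The only overall PFS median that the protocol cites for proton reirradiation is 14 months, which exceeds both the null and the target. If the backbone alone does better than 6 months, the test can reject with no contribution from pembrolizumab. Section 9.3 followed literally would still report that rejection as pembrolizumab benefit. This is the only efficacy comparison with a stated hypothesis and power, so the trial's claim about the drug depends on it.

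**Working it through.** **Inputs.** From Section 9.4: N = 35, accrual A = 24 months, follow-up F = 3 months, one-sided 5%, exponential survival, null median 6 and alternative 10. From Section 1.1: 14 months. Other backbone medians are assumed, to show a range.

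**Step 1: reproduce the planned power.** With hazard λ = ln 2 / median and uniform accrual, expected events are d = N × {1 − [exp(−λF) − exp(−λ(A+F))] / (λA)}.

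- Median 6: λ = 0.1155, d = 35 × 0.761 = 26.6
- Median 10: λ = 0.0693, d = 35 × 0.604 = 21.1
- Median 14: λ = 0.0495, d = 35 × 0.496 = 17.3

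For a Wald test on the log hazard, power = Φ{[ln(m1/m0) − 1.645/√d0] × √d1}. For 6 versus 10 this is Φ{(0.511 − 0.319) × 4.60} = Φ(0.88) = 81%. A cube-root transform gives 79.5%. The stated 80% is reproduced. Rejection needs an estimated median above about 6 × exp(0.319) = 8.3 months, which is below the 10-month target.

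**Step 2: rejection when pembrolizumab adds nothing.** The true median is then the backbone median. At 14 months the same formula gives Φ{(0.847 − 0.319) × 4.17} = Φ(2.20) = 98.6%; other standard approximations give 96.5% to 99.9%. Because the plan names no test, I simulated a one-sample log-rank test, rejecting when (E − O)/√E > 1.645, with 200,000 trials per row:

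| Backbone median (months) | Trials rejecting 6 months |
|---|---|
| 6 | 4% |
| 8 | 39% |
| 8.5 | 50% |
| 10 | 78% |
| 12 | 94% |
| 14 | 98.6% |

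**Step 3: the other Background figure.** A 1-year rate of 51% implies an exponential median of 12 × ln 2 / (−ln 0.51) = 12.35 months, where the test rejects in about 95% of trials. The 51% is a local-only rate, the highest of several reports, and not from protons. It is an optimistic guide to overall PFS and is not relied on here.

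**Step 4: would testing against 14 months repair this?** No, for two reasons.

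- *Power.* With a 14-month null and a true median of 20 months, the same design rejects in only about 36% of trials.
- *Bias.* Patients must be progression-free to start pembrolizumab (Section 8.1.5.3), yet PFS runs from the start of definitive therapy (Section 9.3.1). Three to 8 weeks of radiation plus a 4 to 12 week gap gives an assumed guaranteed progression-free period of 7 to 20 weeks. With a 14-month exponential thereafter and no drug effect, the 14-month null is rejected in about 12.6%, 25% and 55% of trials for 7, 12 and 20 weeks.

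The same selection affects the planned test. With a 6-month exponential after the guaranteed period, the 6-month null is rejected in about 27%, 62% and 98% of trials. The table in Step 2 leaves this out.

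**The case against.** The strongest reply is that 14 months may not be the right benchmark. Section 1.1 describes early outcomes in an initial cohort and gives no cohort size, confidence interval or volume cut-off for low volume. Section 4.1 does not link the 250 cc limit to that cohort. The 6 months is assigned to standard therapy, so the two figures may describe different populations. All of this stands.

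A reader might therefore infer too much in three ways:

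- *That a useless add-on would almost surely pass.* This needs 14 months, or something near it, to be the true backbone median here, which the documents do not establish. At 8 months the figure is 39%.
- *That the protocol contradicts itself.* It does not. It leaves a choice of comparator unexplained.
- *That the primary analysis fails.* It does not. The intention-to-treat analysis estimates median PFS with a 95% CI and has no pass/fail rule.

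The reply does not rescue the claim in Section 9.3. Any backbone median moderately above 6 months takes the false pass rate well beyond 5%. If standard therapy means something other than proton reirradiation, the comparison mixes the effect of protons with that of pembrolizumab. The secondary label limits the scope, but the test is still the stated basis for a conclusion about the drug.

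**Conclusion.** Wrong as written; should be fixed. Rejecting 6 months would show only that PFS under the whole regimen, in patients who reached pembrolizumab, exceeds 6 months. It would not show benefit over proton reirradiation alone. With no pembrolizumab effect, the pass rate runs from about 39% at a backbone median of 8 months to 98.6% at 14, against a nominal 5%. These rates assume exponential PFS, 35 patients, the planned accrual and follow-up, and a one-sample log-rank test, which is my choice. How far up the range this trial lies depends on whether the 14-month cohort resembles its population, and the documents do not settle that. The primary estimate is affected only in how it is read.

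**What to change.** In Sections 9.3 and 9.4:

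1. Delete the statement that this test determines the benefit of adding pembrolizumab. State that rejecting 6 months shows only that PFS of the whole regimen exceeds 6 months, and is not evidence of benefit over proton reirradiation alone.
2. Report the intention-to-treat median PFS and its 95% CI descriptively beside both 6 months and the cited 14 months, together with the range of pass rates in the table above.
3. Either base the null on proton-reirradiation patients comparable on target volume, and redo the power statement, or state why the 14-month cohort does not apply.
4. Do not add a formal test against 14 months in the pembrolizumab-treated subgroup, because of the selection bias in Step 4. State that even without that bias the design has only about 36% power against 14 months at a true median of 20 months.

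The cost is protocol wording and a weaker claim. No new patients are needed.
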